9.7 Pharmacokinetics

Plasma GSK1265744 concentration-time data will be analyzed by noncompartmental methods using WinNonlin Professional 5.2 or higher, Phoenix (Pharsight Corporation) or comparable software. Individual plasma PK parameters for each injection interval will be determined which include the area under the plasma concentration time curve over the dosing interval ($AUC(0-\tau)$), maximum observed concentration (C_{max}), time to maximum observed concentration (t_{max}), concentration at the end of the dosing interval (C_τ), apparent terminal phase half-life for 744LA administration ($t_{1/2}$) and lambda z as a measure of absorption rate constant (λ_z) if data allow among the participants in the 744 arm. The pharmacokinetic parameters will be generated by the scientist from HPTN Core Laboratory.

The summary statistics of pharmacokinetic parameters, $AUC(0-\tau)$, C_{max} , and C_τ , will be presented by injection. The means of the pharmacokinetic parameters (after log-transformation) and their 95% CIs will be displayed by visit weeks and cohort. The pharmacokinetic parameters, $AUC(0-\tau)$, C_{max} , and C_τ in different injection intervals will be compared using paired t-test if the data or log transferred data appear to be normally distributed and using Wilcoxon signed rank test if the data or log transferred data are not normally distributed.

Time to steady state will also be assessed by comparing plasma concentration, C_τ , at Week 41 (following third injection) to previous C_τ concentrations at Weeks 17 and 29 (at Weeks 17, 25, and 29) in Cohort 1 (Cohort 2). General estimation equation (GEE) regression model will be used to test any difference in the concentration over time and a trend.

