9.7.1 Association between Pharmacokinetics and Baseline Characteristics

To evaluate differential pharmacokinetics of 744LA in participants by age, gender, race, ethnicity, weight, body mass index (BMI), and smoking status, we will use GEE regression model to account the correlations of the PK parameters following three injections in Cohort 1 or five injections in Cohort 2. The analysis will be performed separately for each cohort. The associations between the PK parameters and the predictors will be tested in univariate models (include one predictor in each model) and

in a multivariate model (include all predictors). Each model will be adjusted for sites (US vs. Non-US sites) by cohort.

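### The paired-test rule in SAP 9.7 does not decide between the t-test and the Wilcoxon test for skewed PK parameters, and no analysis scale is named for the paired tests or the GEE models

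*SAP*

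**What the plan says.** Section 9.7 treats the three PK parameters on the log scale for display: "The means of the pharmacokinetic parameters (after log-transformation) and their 95% CIs will be displayed by visit weeks and cohort".

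For comparing injection intervals it turns to a normality-dependent rule. The rule reads "compared using paired t-test if the data or log transferred data appear to be normally distributed and using Wilcoxon signed rank test if the data"; its second branch, given here to the end, is the "Wilcoxon signed rank test if the data or log transferred data are not normally distributed". It does not say on which scale the t-test is run, on which scale the signed-rank differences are formed, or how normality is judged. The general rule for within-arm comparisons in 9.3 offers the paired t-test or the Wilcoxon test for continuous variables, again with no scale and no criterion for choosing.

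For steady state, 9.7 states that a "General estimation equation (GEE) regression model will be used to test any difference in the concentration over time and a trend". For baseline characteristics, 9.7.1 states "we will use GEE regression model to account the correlations of the PK parameters following three injections" in Cohort 1 or five in Cohort 2. Neither names a transformation, link or distribution. By contrast, the GEE analysis of sexual behaviour in 9.10 specifies a negative binomial distribution and robust standard errors.

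**The concern.** A rule that picks a test from the look of the data should at least lead to one test. This one leads to two for the kind of data that 9.7 appears to expect, since it plans log-scale means. The analyst must then settle the test and the scale with the data in view.

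The rule covers three parameters. If all pairs of intervals are compared, there are 3 pairs in Cohort 1 and 10 in Cohort 2, so up to 3×3 + 3×10 = 39 such choices.

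Two things are at stake in the secondary PK objectives. First, which interval differences are declared can depend on the choice. Second, the quantity estimated is left open: a raw-scale analysis gives a concentration difference, and a log-scale analysis gives a ratio that matches the log-scale means in the same section. The silence on scale in the GEE models leaves the same question open there.

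**Working it through.** **Step 1: the rule as written.**

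| Raw looks normal | Log looks normal | t-test condition | Wilcoxon condition |
|---|---|---|---|
| yes | yes | met | not met |
| yes | no | met | met |
| no | yes | met | met |
| no | no | not met | met |

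The rule is decisive only when both scales agree. Log-normal data fall in the third row.

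**Step 2: inputs for the size.** The SAP states no PK variability, effect size or power, so there is no figure to reproduce. From Section 2.4: 82 active participants in Cohort 1 and about 66 in Cohort 2, both upper bounds for the number of pairs. Assumed: log-normal values, CV 30%, 50% or 80%, within-participant correlation 0.5, ratio between intervals 1.15 or 1.25, two-sided 5%. Shapiro-Wilk at 0.05 stands in for the undefined normality criterion. There were 2,000 runs per setting, so a power near 50% has a simulation error of √(0.5×0.5/2000) ≈ 1.1 points.

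**Step 3: check of the simulation.** The log-SD is s = √ln(1+CV²). With correlation 0.5, the SD of a log difference is s·√(2(1−0.5)) = s. For CV 80%, s = √ln(1.64) = 0.703. With n = 82 and ratio 1.15, ln(1.15)·√82/0.703 = 0.1398×9.055/0.703 = 1.80, and power ≈ Φ(1.80−1.96) ≈ 44%. The simulation gave 44.6%.

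**Step 4: t-test on logs against signed-rank on raw differences.**

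| n | CV | Ratio | Log t, % | Signed-rank, % | Gap, points | Both branches met, % | Tests disagree, % |
|---|---|---|---|---|---|---|---|
| 82 | 30% | 1.15 | 98.4 | 98.2 | 0.2 | 86.0 | 1.0 |
| 82 | 50% | 1.15 | 74.3 | 71.6 | 2.7 | 90.4 | 8.8 |
| 82 | 80% | 1.15 | 44.6 | 38.1 | 6.5 | 91.1 | 12.0 |
| 82 | 80% | 1.25 | 82.2 | 75.4 | 6.8 | 90.0 | 10.4 |
| 66 | 30% | 1.15 | 96.7 | 95.8 | 0.9 | 81.8 | 2.0 |
| 66 | 50% | 1.15 | 66.7 | 62.0 | 4.7 | 90.1 | 9.5 |
| 66 | 80% | 1.15 | 36.2 | 31.0 | 5.2 | 90.5 | 13.0 |
| 66 | 80% | 1.25 | 72.0 | 65.0 | 7.0 | 90.5 | 12.6 |

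Disagreement vanishes where power is close to 100%. A second set of runs used ratio 1.15 with between- and within-participant log-SDs of 0.35/0.25, 0.5/0.3 and 0.7/0.4. Both branches were met in about 90% of trials and the tests disagreed in about 3-15%.

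**Step 5: the same rule read as Wilcoxon only if neither scale is normal.** On the second set of assumptions, trying raw t, then log t, then Wilcoxon:

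| n | Power under this reading, % | Power of log t always, % |
|---|---|---|
| 82 | 94.1 / 84.3 / 59.9 | 94.1 / 84.7 / 60.6 |
| 66 | 87.0 / 75.3 / 48.5 | 87.2 / 75.7 / 48.9 |

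The loss is 0 to 0.7 points. For n = 82, raw values passed the normality check in 0.2%, 0.0% and 0.0% of trials.

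**Step 6: GEE, if the outcome were left raw.** Assumed: within-participant correlation 0.6, a binary predictor with 60% in one group (the share of women in 4.1), identity link, robust SE, 5,000 runs. Power, log against raw:

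- n = 82: CV 30%, ratio 1.25, 98% against 97%; CV 50%, ratio 1.25, 70% against 68%; CV 80%, ratio 1.5, 86% against 80%; CV 120%, ratio 0.67, 62% against 45%.
- n = 66: CV 30%, ratio 1.25, 95% against 95%; CV 120%, ratio 0.67, 54% against 40%.

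For a predictor with 20% prevalence, separate runs gave the log scale 8 to 15 points more power for ratios above 1, but 0 to 8 points less for ratios below 1.

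**The case against.** The strongest reply is that the rule has an ordinary reading: t-test where either scale is normal, Wilcoxon where neither is. Section 9.3 uses a similar normal-or-not pattern for comparisons between arms. On that reading log-normal parameters go to a t-test on logs, and Step 5 shows that almost nothing is lost. If normality is judged on the paired differences instead, the loss is still only 0.3 to 2.9 points. This stands as a sensible intention, but the text does not say it: the Wilcoxon branch repeats the same either/or wording, and an analyst following it literally could justify either test.

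Two stronger readings are tempting and should not be drawn. A reader might infer that the GEE models use untransformed values, because "regression model will be used to test any difference in the concentration over time and a trend" mentions only the concentration and 9.7.1 only the parameters. The SAP is silent on this, and the log-scale means in the same section make a log outcome at least as natural.

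A reader might also infer a loss of some 4 to 19 points, by comparing a log t-test with a raw t-test on log-normal data. The rule allows a t-test only where normality appears to hold, and raw values almost never pass in that setting, so the plan would hardly ever take that path.

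It is also fair that every magnitude here is assumed and that only secondary analyses are affected.

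**Conclusion.** The point holds as a defect of specification. The overlap between the two branches follows from the text alone and needs no simulation.

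Its size depends on how the overlap is resolved. It is under 1 point of power if Wilcoxon is kept for data normal on neither scale, and about 1 to 7 points if the overlap goes to Wilcoxon on raw differences. The two tests give different significance calls in about 3-15% of trials. These figures rest on log-normal data and assumed variability, and they shrink to nothing where power is near 100%.

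For the GEE models the finding is only that the scale is unstated. Any loss from a raw-scale model is conditional: negligible at low variability, material at high variability (17 points at CV 120% with ratio 0.67 and n = 82), and of mixed direction for low-prevalence predictors. The case for fixing the scale there rests on consistency of the estimated quantity more than on power.

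The primary safety and tolerability endpoints are untouched. This is a cheap improvement that should be made.

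**What to change.** In 9.7, replace the normality-dependent choice with a fixed analysis: AUC(0-tau), Cmax and C-tau are natural-log transformed, injection intervals are compared by paired t-test on the log scale, and results are reported as geometric mean ratios with 95% CIs. Keep the signed-rank test on log differences as a sensitivity analysis only.

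For consistency, state in the C-tau GEE of 9.7 and in the GEE of 9.7.1 that the outcome is the log-transformed parameter and that coefficients are reported as geometric mean ratios with 95% CIs.

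The cost is a few sentences and no new data; Section 1 allows the SAP to be updated before the interim and final analyses. There are two small downsides: effects are read as ratios rather than concentration differences, and values below quantification need a stated handling before logging.

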2.4 Schema

Cohort 1

W = Week

Cohort 2

The 110 participants in Cohort 1 and 90 participants in Cohort 2 were randomized to one of the two study arms with an active GSK 744 to placebo ratio of 3:1, stratified by gender and region (US and non US), as follows:

Cohort 1

Arm 1: 82 participants received daily oral 744 (30 mg tablets) for 4 weeks, followed by an one week washout period, to establish safety and tolerability, followed by intra-muscular (IM) gluteal injections of 800 mg of 744LA (administered as two sequential 400 mg gluteal injections) at three time points at 12 week intervals as: Week 5, Week 17, and Week 29.

Arm 2: 28 participants received daily oral matching placebo and IM injections of vehicle-matched placebo on the same schedule as Arm 1.

Cohort 2

Arm 1: Approximately 66 participants will receive daily oral 744 (30 mg tablets) for 4 weeks, followed by a one week washout period, to establish safety and tolerability, followed by intra-muscular (IM) gluteal injections of 600 mg of 744LA (administered as one 600 mg gluteal injection) at five time points at 4 and 8 week intervals as: Week 5, Week 9, Week 17, Week 25, and Week 33.

Arm 2: Approximately 22 participants will receive daily oral matching placebo and IM injections of vehicle-matched placebo on the same schedule as Arm 1.

All participants will receive HIV testing with pre- and post-test counseling, in addition to risk-reduction counseling and condoms and lubricant. All participants will be followed according to the Schedule of Evaluations and Procedures provided in HPTN077 protocol Appendices I-IV.

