4.4 Study Visits

Cohort 1:

- Week 0: enrollment visit
- Weeks 2 and 4: oral phase safety visits
- Week 5: the first injection visit
- Weeks 6, 9, 13: safety visits after the 1st injection
- Week 17: the second injection visit
- Weeks 18 and 23: safety visits after the 2nd injection
- Week 29: the third injection
- Weeks 30, and 35: safety visits after the 3rd injection
- Week 41: primary endpoint visit
- Weeks 53, 65, 77, 89, 101: tail phase safety visit
- Week 105: final study visit.

Cohort 2:

- Week 0: enrollment visit
- Weeks 2 and 4: oral phase safety visits
- Week 5: the first injection visit
- Week 6: safety visits after the 1st injection
- Week 9: the second injection visit
- Weeks 10 and 13: safety visits after the 2nd injection
- Week 17: the third injection visit
- Weeks 18 and 21: safety visits after the 3rd injection
- Week 25: the forth injection
- Weeks 26, and 29: safety visits after the 4th injection
- Week 33: the fifth injection visit
- Week 34 and 37: safety visits after the 5th injection
- Week 41: primary endpoint visit
- Weeks 53, 65, 77, 89, 101: tail phase safety visit
- Week 109: final study visit.

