5.2 Interim Analysis

An interim analysis will be performed when 50% of the participants have completed their primary endpoint visit (Week 41). All data available at that time will be included in the analysis. Pharmacokinetic data will be analyzed when approximately 50% of Cohort 1 reaches Week 29 (two troughs) for Cohort 1 participants, and when approximately 50% of Cohort 2 reaches Week 17 (two troughs) for Cohort 2.

With the approval from HPTN SMC, the unblinded summaries of the safety and pharmacokinetic data from the analysis may also be provided to the key members of the protocol team and possibly to regulatory agencies to facilitate an initiation of a phase III trial. All members of the protocol team, including GSK and ViiV Healthcare, as well as study participants will remain blinded to individual participant treatment assignment. The data from this analysis may also be combined with the interim data from a similar study being conducted by GSK/ViiV, if needed and appropriate. Pooled summaries will also be provided to the study team to share with regulators.

To maintain the integrity of the clinical study, only the following staff may be unblinded at these SMC interim analyses, as deemed necessary by the SMC: selected clinical

pharmacometrist, programmer, and statisticians who will use unblinded 744 concentrations to build the population PK models, and staff who will incorporate safety data from this analysis into regulatory documents for other studies of 744. The primary study team (medical monitor, clinical study team leader, operational scientist, data manager) should remain blinded until all subjects complete the week 41 visit and the data has been entered and cleaned and all major protocol violators have been identified. The primary study team will only receive unblinded summary tables and figures for the planned interim analysis.

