11.3 Pharmacokinetic and Other Secondary Analyses

11.3.1 List of Tables

Table 21 Summary of pharmacokinetic parameters by injection

Table 22 Assess the time to steady state of the plasma drug concentration, C_{τ}

Table 23 Associations of sex at birth (or BMI) with pharmacokinetic parameters

Table 24 Change in sexual risk behavior (number of sexual partners) from baseline

Table 25 HIV incidences during the study

Table 26 Reported pregnancies by treatment arm and cohort

Table 27 The proportion of women experiencing any Grade 2 or higher AEs (a) prior to completion of the full oral phase and (b) prior to completion of the full injection phase --- among the women who use any injectable hormonal contraception (combined cohort)

Table 28 The proportion of the women who discontinue the study product for reasons of toxicity, tolerability, or acceptability (a) prior to completion of the full oral phase and (b) prior to completion of the full injection phase—among the women who use any injectable hormonal contraception

Table 29 Summary of pharmacokinetic parameters by injection and cohort —among the women who use any injectable hormonal contraception

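### The Cohort 2 steady-state comparison treats Week 29 as an end-of-interval concentration, but Week 29 is mid-interval, and the actual trough at Week 33 is left out

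*SAP*

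**What the plan says.** SAP 9.7 (Pharmacokinetics) derives Cτ for each injection interval and defines it as the "concentration at the end of the dosing interval". For time to steady state, it compares Cτ at Week 41, described as following the third injection, with earlier Cτ "concentrations at Weeks 17 and 29 (at Weeks 17, 25, and 29) in Cohort 1 (Cohort 2"). A GEE model then tests for any difference over time and for a trend. The result goes into Table 22 (SAP 11.3.1): "Assess the time to steady state of the plasma drug concentration".

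The schedule stands elsewhere in the SAP. Section 2.4 gives the Cohort 2 injections as "Week 5, Week 9, Week 17, Week 25, and Week 33". Section 4.4 lists, for Cohort 2, "Weeks 26, and 29: safety visits after the 4th injection" and then "Week 33: the fifth injection visit".

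Section 5.2 times the interim pharmacokinetic analysis by counting troughs. The five-injection cohort is analysed "when approximately 50% of Cohort 2 reaches Week 17 (two troughs) for Cohort 2"; the matching trigger for the three-injection cohort is that "approximately 50% of Cohort 1 reaches Week 29 (two troughs) for Cohort 1 participants".

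**The concern.** A steady-state check compares concentrations taken at the same point of successive equal dosing intervals. If one of them is taken halfway through an interval, the comparison picks up the ordinary decline between doses as well as any accumulation.

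For Cohort 2 the list includes Week 29, which section 4.4 describes as a safety visit after the fourth injection. It omits Week 33, the last trough before Week 41 and the most informative one for whether concentrations have levelled off. An analyst who follows the list literally could report that steady state had not been reached when it had.

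The description of Week 41 as following the third injection also fits only Cohort 1. In Cohort 2, Week 41 follows the fifth.

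**Working it through.** **Step 1. Interval ends from the SAP's schedule.** Each interval ends at the next injection visit, and Week 41 closes the last one.

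| Cohort | Injection weeks (2.3, 2.4, 4.4) | Interval ends | Interval lengths (weeks) | Weeks used in 9.7 |
|---|---|---|---|---|
| 1 | 5, 17, 29 | 17, 29, 41 | 12, 12, 12 | 17, 29, 41 |
| 2 | 5, 9, 17, 25, 33 | 9, 17, 25, 33, 41 | 4, 8, 8, 8, 8 | 17, 25, 29, 41 |

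The rule reproduces the Cohort 1 list exactly. It also reproduces both trough counts in 5.2: Weeks 17 and 29 by Week 29 in Cohort 1, and Weeks 9 and 17 by Week 17 in Cohort 2. It fails only for the Cohort 2 list in 9.7.

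**Step 2. Weeks since the last injection, Cohort 2.** Week 17: 17 − 9 = 8. Week 25: 25 − 17 = 8. Week 29: 29 − 25 = 4. Week 33: 33 − 25 = 8. Week 41: 41 − 33 = 8. Week 29 is the odd one out. Omitting Week 9 is defensible, because it closes the single 4-week interval.

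**Step 3. Illustrative size.** These inputs are assumptions, because the SAP gives no half-life or SD:
- log-linear decline between 4 and 8 weeks after injection, with half-life h of 4, 6, 8 or 12 weeks;
- SD of a paired log difference of 0.4 or 0.6, with independent errors (so the variance of one log value is SD²/2);
- n = 66 (the approximate Cohort 2 active arm in 2.4) or n = 50 to allow for losses.

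At true steady state the Week 29 value exceeds a trough by the factor 2^(4/h), that is, by d = ln 2 × 4/h on the log scale.

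| h (weeks) | Week 29 / trough | Week 41 / Week 29 |
|---|---|---|
| 4 | 2.00 | 0.50 |
| 6 | 1.59 | 0.63 |
| 8 | 1.41 | 0.71 |
| 12 | 1.26 | 0.79 |

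*Week 41 versus Week 29 contrast*, z = d/(SD/√n). At h = 12, d = 0.231:
- n = 66, SD 0.4: 0.231/(0.4/√66) = 4.69;
- n = 50, SD 0.6: 0.231/(0.6/√50) = 2.72.

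*Any-difference test over four visits* (3 df, two-sided 5% level). The log means are (0, 0, d, 0), whose sum of squares about their mean is 0.75d². The noncentrality is n × 0.75d²/(SD²/2):
- n = 66, SD 0.4: 33.0, rejection probability 0.999;
- n = 50, SD 0.6: 11.1, rejection probability 0.81.

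*Linear trend, time in weeks.* Weeks 17, 25, 29 and 41 have mean 28 and sum of squares 121 + 9 + 1 + 169 = 300. Week 29 lies 1 week from the mean, so the spurious slope is d/300 per week. Over 24 weeks this is exp(24d/300) − 1, or 5.7% at h = 4 and 1.9% at h = 12. At n = 66 and SD 0.4, z is 1.15 to 0.38.

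*Linear trend, visits coded 1 to 4.* The sum of squares is 5, the spurious slope is 0.5d/5 = 0.1d, and its standard error is √(0.08/(66 × 5)) = 0.0156. Then z is 4.45 at h = 4 and 1.48 at h = 12.

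**Step 4. After the correction.** With Weeks 17, 25, 33 and 41 every value is 8 weeks post-dose. At steady state d = 0 and the bias disappears.

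**The case against.** The best counter-argument is that this is a slip that would correct itself. Section 9.7 already derives Cτ for every injection interval, Table 21 summarises the parameters by injection, and 9.7.1 models all five Cohort 2 injections. The trough for the interval from Week 25 to Week 33 is therefore planned elsewhere, and an analyst working from the per-interval Cτ variable would find no Week 29 value. That is fair, and it limits the omission of Week 33 to the steady-state comparison. But the week list is explicit, nothing in the SAP corrects it, and the raw Week 29 concentration, if sampled, could be used in its place.

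The size rests on assumed inputs, and the 12-week half-life is not a floor. At 24 weeks, by the same formulas, the ratio is 1.12. With n = 50 and SD 0.6 the contrast is 1.36 SE and the any-difference test rejects with probability 0.26; with n = 66 and SD 0.4 it rejects with probability 0.67. The direction of the bias holds, but its size is illustrative. The reassurance about the trend is also conditional: the SAP does not fix the time coding for this model, and coding visits 1 to 4 makes the distortion larger.

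The protocol's pharmacokinetic sampling schedule is not at hand, so a pre-injection sample at Week 33 is assumed. Without one, Week 29 would still not meet the SAP's definition of Cτ. The description of Week 41 as following the third injection is editorial, since Week 41 is the right final trough in both cohorts.

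**Conclusion.** The concern holds. The Cohort 2 week list in 9.7 contradicts the SAP's own definition of Cτ, its injection schedule and its trough count in 5.2. This follows from the schedule alone and needs no assumption.

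The consequence is a bias towards a false change in the Week 41 versus Week 29 contrast and in the GEE test of any difference. For half-lives of 4 to 12 weeks, under the stated assumptions, it is large enough to mislead; for longer half-lives it shrinks. The comparisons of Week 41 with Weeks 17 and 25 remain valid, and a trend with time in weeks is little affected. The harm is confined to one secondary pharmacokinetic analysis (Table 22); the primary safety and tolerability analyses are untouched. It should be fixed, but it does not threaten the trial's main conclusions.

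**What to change.** In SAP 9.7 and the shell for Table 22, compare Cohort 2 Cτ at Week 41 with Cτ at Weeks 17, 25 and 33, and remove Week 29. State that Week 41 follows the third injection in Cohort 1 and the fifth in Cohort 2. Leave the Cohort 1 list unchanged. Confirm against the protocol's sampling schedule that Week 33 has a pre-injection sample; a participant without one is missing that trough, and Week 29 should not stand in for it.

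A useful clarification in the same section concerns the paired comparisons between injection intervals. They do not set apart Cohort 2's first interval, which is 4 weeks against 8 for the rest; at equal average concentration, AUC over 8 weeks is twice AUC over 4 weeks. Restrict the Cohort 2 comparisons of AUC(0–τ) and Cτ to the 8-week intervals. Dividing AUC by τ would allow the first interval to be included for AUC, but it does not make Cτ comparable.

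The cost is SAP wording only: one week number, one parenthesis and one sentence. No visit, dose or data collection changes.

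### The tests planned for time to steady state (SAP 9.7, Table 22) cannot show when trough levels become stable; trough ratios with intervals and a stated criterion are needed

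*SAP*

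**What the plan says.** SAP section 9.7 has three elements that bear on this point.

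- **The comparison.** "Time to steady state will also be assessed by comparing plasma concentration" (C_tau) at Week 41 with earlier values "at Weeks 17 and 29 (at Weeks 17, 25, and 29) in Cohort 1 (Cohort 2"). The model for this follows: "General estimation equation (GEE) regression model will be used to test any difference in the concentration over time and a trend".
- **Paired tests.** AUC, C_max and C_tau "in different injection intervals will be compared using paired t-test", or by the Wilcoxon signed rank test if not normally distributed.
- **Intervals.** Means of the log-transformed parameters "and their 95% CIs will be displayed by visit weeks and cohort".

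The output is Table 22 in section 11.3.1, titled "Assess the time to steady state of the plasma drug concentration". Neither section gives a margin, an interval for the ratio of two troughs, an order in which troughs are compared, or a rule that turns the results into a time. The scale of the GEE outcome is not stated.

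**The concern.** Time to steady state asks from which trough onwards levels stop changing by an amount that matters. A test of equality over all listed weeks asks something else: whether every trough has the same mean. It can be significant because of early accumulation alone, and then it does not say whether the later troughs are stable. If it is not significant, that may reflect stability, or only variability and missing samples. Table 22 would then carry p-values that depend on the first trough and on the number of participants with PK data, with no estimate of how far the last trough still differs from the one before.

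**Working it through.** The SAP states no power, variability or margin for this analysis, so there is no planned figure to reproduce. The check covers Cohort 1, whose three dosing intervals end at Weeks 17, 29 and 41.

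**Inputs from the SAP (section 2.4).** Active arms: "Arm 1: 82 participants received daily oral 744 (30 mg tablets) for 4 weeks" in Cohort 1 and "Arm 1: Approximately 66 participants will receive daily oral 744 (30 mg tablets) for 4 weeks" in Cohort 2. Both are upper limits for the PK analysis; n = 70 lies between them.

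**Assumptions.** Log-normal C_tau, complete data, equal variances and correlations across troughs, two-sided 5% tests, within-person CV of 30, 45 or 60%.

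**Step 1: what the trend test measures.** With three equally spaced visits and complete data, the linear contrast has weights −1, 0, +1. The trend is therefore Week 41 minus Week 17, and Week 29 has no weight. It cannot separate a plateau from Week 29 onwards from a continuing rise.

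**Step 2: standard error.** The within-person log SD is s = √ln(1 + CV²), and a difference between two troughs has SE = s·√(2/n). At CV 45%, s = √ln(1.2025) = 0.429 and SE = 0.429 × √(2/70) = 0.0726.

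**Step 3: true plateau from the second trough (1 : 1.25 : 1.25).**
- Trend: power = Φ(ln 1.25/SE − 1.96). At CV 45% this is Φ(0.2231/0.0726 − 1.96) = Φ(1.11) = 87%.
- Overall 2-df test: noncentrality = n·(2/3)(ln 1.25)²/s² = 70 × 0.0332/0.1844 = 12.6, which gives 90%.
- Week 41 versus Week 29: rejects at its nominal 5%.

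**Step 4: last step still rising 15%, tested by Week 41 versus Week 29.** Missed = 1 − Φ(ln 1.15/SE − 1.96). At CV 45% this is 1 − Φ(0.1398/0.0726 − 1.96) = 1 − Φ(−0.03) = 51%.

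**Step 5: what an interval would give.** The 90% CI for the ratio extends by a factor exp(1.645·SE) either side. If the true ratio is 1, it lies within 0.80 to 1.25 with probability 2Φ(0.2231/SE − 1.645) − 1.

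| n = 70, within-person CV | 30% | 45% | 60% |
|---|---|---|---|
| SE of log ratio | 0.0496 | 0.0726 | 0.0937 |
| Plateau from 2nd trough: trend rejects | 99% | 87% | 66% |
| Plateau from 2nd trough: overall test rejects | 100% | 90% | 69% |
| 15% last-step rise missed by Week 41 v Week 29 | 20% | 51% | 68% |
| 90% CI factor | 1.09 | 1.13 | 1.17 |
| Chance that the CI fits 0.80–1.25 if the ratio is 1 | >99% | 85% | 54% |

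Simulation of the same patterns gave 99/86/65% for the trend, 100/90/70% for the overall test and 20/53/69% for the missed rise.

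**Step 6: other assumptions.** With n = 82, between-subject CV 40 to 80% and correlation 0.5 to 0.7, a 1 : 1.3 : 1.3 pattern is rejected by the overall test in 95 to 100% and by the trend test in 92 to 100%. A simulated GEE fit with robust standard errors (CV 60%, correlation 0.6) gave 100% and 99.8%.

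**Step 7: Cohort 2 time points.** By section 4.4 injections are at Weeks 5, 9, 17, 25 and 33, so dosing intervals end at Weeks 9, 17, 25, 33 and 41. Section 5.2 agrees, counting two troughs by Week 17. Section 9.7 lists Weeks 17, 25 and 29 before Week 41. Weeks 9 and 33 are absent, and Week 29 is a safety visit four weeks after the fourth injection, in mid-interval. The sentence also ties Week 41 to the third injection; in Cohort 2 it follows the fifth. The arithmetic above therefore does not carry over to Cohort 2 as listed.

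**The case against.** The strongest reply is that section 9.7 does not rely on the overall and trend tests alone. It compares Week 41 with each earlier C_tau and plans paired tests between injection intervals. The Week 41 versus Week 29 contrast excludes the first trough and is not disturbed by early accumulation. This stands, and it limits the dating problem to the GEE tests. The contrast still favours a plateau only by not rejecting, and nothing says which result governs if the tests disagree.

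Three stronger readings are tempting and are not supported.

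- A reader might infer that the plan declares steady state whenever the test is not significant. Neither section 9.7 nor Table 22 says so; the criterion is missing, not wrongly stated.
- A reader might infer that no intervals are planned, or that the GEE is run on the untransformed scale. CIs of the log-scale means by visit are planned, although these are not intervals for a within-person ratio, and the GEE scale is simply unstated.
- A reader might conclude that a non-significant result carries no information. With a steady 10% rise per interval and n = 82, the trend test detects it in 69% to more than 99% of trials under the assumptions of step 6. The Week 41 versus Week 29 comparison misses it in 18 to 77%. Non-significance is weak evidence, not empty.

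It is also fair that a flat second step followed by a 15% rise would be unusual for ordinary accumulation. The missed-rise figures do not need that pattern, since they concern the last step alone. Finally, time to steady state is not a listed secondary endpoint in section 3.2, and the SAP ties no decision to it.

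**Conclusion.** The concern holds in limited form. In Cohort 1 the overall and trend tests cannot date steady state, because they reject after a first-step rise even when levels are flat thereafter. The one comparison that avoids this gives only weak support for a plateau: at n = 70 a true 15% last-step rise is missed in about 20% of trials at CV 30% and in about half to two thirds at CV 45 to 60%. These percentages rest on assumed variability and complete data, since the SAP gives neither. That the trend ignores Week 29 needs no variability assumption, only complete data and equal spacing. In Cohort 2 the listed weeks do not match the ends of the dosing intervals and need reconciling before any contrast is run. The matter is confined to one supportive PK table; the primary safety and tolerability endpoints are untouched.

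**What to change.** 1. Reconcile the Cohort 2 weeks in section 9.7, and the injection to which Week 41 is tied, with the visit schedule in section 4.4.
2. State that C_tau is analysed on the log scale.
3. In Table 22 report, by cohort, the within-person geometric mean ratio of the last to the previous trough, then stepwise backwards to earlier troughs, each with a 90% CI.
4. Pre-state the margin against which these intervals are judged, and define steady state as reached from the earliest trough at which the criterion is met and stays met. A range of 0.80 to 1.25 is an illustration only; the team should choose and justify its own.
5. State that steady state is not inferred from a non-significant test. The GEE tests may stay as description.

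The cost is a few lines of SAP text and a revised layout for one table, with no new data. The downside is that with high variability the interval may not fit the margin: at n = 70 and CV 60% it would fit 0.80 to 1.25 in only about 54% of trials even if the true ratio were 1. Steady state would then be reported as unproven.
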